8.2 Safety assessments

Planned timepoints for all safety assessments are provided in [Table 1](#) and [Table 2](#).

8.2.1 Clinical safety laboratory assessments

Blood and urine samples for determination of clinical chemistry, haematology, and urinalysis will be taken at the times indicated in the assessment schedules and as clinically indicated (see [Table 1](#) and [Table 2](#)).

Clinical laboratory safety tests, including serum pregnancy tests, will be performed in a licensed clinical laboratory according to local standard procedures. Sample tubes and sample sizes may vary depending on the laboratory method used and routine practice at the site. Urine pregnancy tests may be performed at the site using a licensed test (urine or serum pregnancy test). Abnormal clinically significant laboratory results should be repeated as soon as possible (preferably within 24 to 48 hours).

Additional safety samples may be collected if clinically indicated at the discretion of the Investigator. The date, time of collection, and results (values and units) will be recorded on the appropriate eCRF page.

The laboratory variables to be measured are presented in [Table 10](#) (clinical chemistry), [Table 11](#) (haematology), and [Table 12](#) (urinalysis).

Other safety assessments to be performed at screening include HbsAg, hepatitis C antibodies, and HIV antibodies.

The following laboratory variables will be measured.

Table 10 Clinical chemistry

| | |
|--|--|
| Albumin | Lactate dehydrogenase |
| Alkaline phosphatase ^a | Lipase ^b |
| ALT ^a | Magnesium ^c |
| Amylase ^b | Potassium |
| AST ^a | Sodium |
| Bicarbonate ^c | Total bilirubin ^a |
| Calcium | Total protein |
| Chloride ^c | TSH ^d |
| Creatinine | T3 free ^e (reflex) |
| Creatinine clearance | T4 free ^e (reflex) |
| Gamma glutamyltransferase ^c | Urea or blood urea nitrogen, depending on local practice |
| Glucose | |

^a Tests for ALT, AST, alkaline phosphatase, and total bilirubin must be conducted and assessed concurrently. If total bilirubin is $\geq 2 \times$ ULN (and no evidence of Gilbert's syndrome) then fractionate into direct and indirect bilirubin.

^b It is preferable that both amylase and lipase parameters are assessed. For sites where only 1 of these parameters is routinely measured, then either lipase or amylase is acceptable.

^c Bicarbonate (where available), chloride, gamma glutamyltransferase, and magnesium testing are to be performed at baseline, on Day 1 (unless all screening laboratory clinical chemistry assessments are performed within 3 days prior to Day 1), and if clinically indicated.

^d If TSH is measured within 14 days prior to Day 1 (first IP dose administration), it does not need to be repeated at Day 1.

^e Free T3 or free T4 will only be measured if TSH is abnormal or if there is a clinical suspicion of an AE related to the endocrine system.

ALT: Alanine aminotransferase; AST: Aspartate aminotransferase; IP: Investigational product; T3: Triiodothyronine; T4: Thyroxine; TSH: Thyroid-stimulating hormone; ULN: Upper limit of normal.

Table 11 Haematology

| | |
|--|--|
| Absolute neutrophil count ^a | Absolute lymphocyte count ^a |
| Haemoglobin | Platelet count |
| Total white cell count | Coagulation ^b |

^a Can be recorded as absolute counts or as percentages. Absolute counts will be calculated by Data Management if entered as percentage. Total white cell count, therefore, has to be provided.

- ^b For coagulation parameters, activated partial thromboplastin time (either as ratio or as an absolute value in seconds) and international normalised ratio are to be assessed at baseline on Day 1 and as clinically indicated.

Table 12 Urinalysis

| | |
|-----------------------|------------------|
| Bilirubin | Ketones |
| Blood | pH |
| Colour and appearance | Protein |
| Glucose | Specific gravity |

Note: Microscopy is preferred to investigate white blood cells and use the high-power field for red blood cells, dipstick can be used as well.

Note: Urinalysis should be done at baseline (screening) and then as clinically indicated.

If a patient shows an AST or ALT $\geq 3 \times$ ULN together with total bilirubin $\geq 2 \times$ ULN, refer to [Appendix E](#) for further instructions for cases of increases in liver biochemistry and evaluation of Hy's law (HL). These cases should be reported as SAEs if, after evaluation, they meet the criteria for a HL case or if any of the individual liver test parameters fulfil any of the SAE criteria.

All patients should have further chemistry profiles performed at 30 days (± 3 days), 2 months (± 1 week) and 3 months (± 1 week) after last dose of IP (see [Table 2](#)).

Any clinically significant abnormal laboratory values should be repeated as clinically indicated and recorded on the eCRF. Situations in which laboratory safety results should be reported as AEs are described in [Section 8.3.7](#).

All patients with Grade 3 or 4 laboratory values at the time of completion or discontinuation from IP must have further tests performed until the laboratory values have returned to Grade 1 or 2, unless these values are not likely to improve because of the underlying disease.

8.2.2 Physical examinations

Physical examinations will be performed according to the assessment schedules (see [Table 1](#) and [Table 2](#)). Full physical examinations will include assessments of the head, eyes, ears, nose, and throat and the respiratory, cardiovascular, GI, urogenital, musculoskeletal, neurological, dermatological, haematologic/lymphatic, and endocrine systems. Height will be measured at screening only. Targeted physical examinations are to be utilised by the Investigator on the basis of clinical observations and symptomatology. Targeted physical examinations during the treatment cycles (C1 onwards) are not required for asymptomatic patients. Situations in which physical examination results should be reported as AEs are described in [Section 8.3.7](#).

8.2.3 Vital signs

Vital signs (blood pressure [BP], pulse, temperature, and respiratory rate) will be evaluated according to the assessment schedules (see [Table 1](#) and [Table 2](#)). Body weight is also recorded at each visit along with vital signs. The following timepoints for vital signs assessments apply to infusions of durvalumab (MEDI4736).

First IP dose administration

On the day of first IP dose administration, patients will be monitored and vital signs will be collected/recorded in the eCRF prior to, during, and after infusion of IP as presented in the bulleted list below.

BP and pulse, and other vital signs (including temperature and respiratory rate) will be collected before, during, and after IP infusion at the following times (based on a 60-minute \pm 10 minutes infusion):

- Prior to the beginning of the infusion (measured once from approximately 30 minutes before up to 0 minute [ie, the beginning of the infusion])
- Approximately 30 minutes during the infusion (**halfway** through infusion)
- At the end of the infusion (approximately 60 minutes \pm 10 minutes)
- A 1-hour observation period is recommended after the first infusion of IP. If no clinically significant infusion reactions are observed during or after the first cycle, subsequent infusion observation periods can be at the Investigator's discretion (suggested 30 minutes after each IP infusion).

If the infusion takes longer than 60 minutes, then BP and pulse measurements should follow the principles as described above or be taken more frequently if clinically indicated. Additional monitoring with assessment of vital signs will be at the discretion of the Investigator per standard clinical practice or as clinically indicated.

Subsequent IP dose administrations

BP, pulse, and other vital signs (including temperature and respiratory rate) should be measured and collected/recorded in the eCRF prior to the start of the infusion. Patients should be carefully monitored and BP and other vital signs should be measured during and post infusion as per institution standard and as clinically indicated. Any clinically significant changes in vital signs should be entered in an unscheduled vital signs eCRF page.

Situations in which vital signs results should be reported as AEs are described in [Section 8.3.7](#). For any AEs of infusion reactions, please enter the vital signs values into the eCRF.

8.2.4 Electrocardiograms

Resting 12-lead ECGs will be recorded at screening and as clinically indicated throughout the study (see Table 1). ECGs should be obtained after the patient has been in a supine position for 5 minutes and recorded while the patient remains in that position.

In case of clinically significant ECG abnormalities, including a QT interval corrected for heart rate using Fridericia's formula (QTcF) value >470 ms, 2 additional 12-lead ECGs should be obtained over a brief period (eg, 30 minutes) to confirm the finding.

Situations in which ECG results should be reported as AEs are described in Section 8.3.7.

8.2.5 Early patient review for safety

Patients should be contacted every 2 weeks (± 3 days) after receiving IP during the first 3 cycles (Cycle 1 Day 14 ± 3 , Cycle 2 Day 14 ± 3 , and Cycle 3 Day 14 ± 3) to ensure early identification and management of toxicities. This contact should be documented in the medical record.

8.2.6

CCI

CCI

CCI

8.2.7 Other safety assessments

If new or worsening pulmonary symptoms (eg, dyspnoea) or radiological abnormality suggestive of pneumonitis/ILD is observed, toxicity management as described in detail in the Dosing Modification and Toxicity Management Guidelines (see Section 8.4.5.1) will be applied. The results of the full diagnostic workup (including high-resolution computed tomography [HRCT]), blood and sputum culture, haematological parameters, etc) will be captured in the eCRF. It is strongly recommended to perform a full diagnostic workup, to

exclude alternative causes such as lymphangitic carcinomatosis, infection, allergy, cardiogenic oedema, or pulmonary haemorrhage. In the presence of confirmatory HRCT scans where other causes of respiratory symptoms have been excluded, a diagnosis of pneumonitis /ILD should be considered and the Dosing Modification and Toxicity Management Guidelines (Section 8.4.5) should be followed.

Pneumonitis (Interstitial lung disease) investigation

The following assessments, and additional assessments if required, will be performed to enhance the investigation and diagnosis of potential cases of pneumonitis. The results of the assessment (including images) will be collected.

- Physical examination
 - Signs and symptoms (cough, shortness of breath and pyrexia, etc) including auscultation for lung field will be assessed.
- Peripheral oxygen saturation (SpO₂)
- Other items
 - When pneumonitis (ILD) is suspected during study treatment, the following markers should be measured where possible:
 - ILD Markers (KL-6, SP-D) and β -D-glucan
 - Tumour markers: Particular tumour markers that are related to disease progression
 - Additional Clinical chemistry: C-reactive protein (CRP), lactate dehydrogenase (LDH)

8.3 Collection of adverse events

The Investigator is responsible for ensuring that all staff involved in the study are familiar with the content of this Section.

The definitions of an AE and SAE can be found in [Appendix B](#).

AE will be reported by the patient (or, when appropriate, by a caregiver, surrogate, or the patient's legally authorised representative).

The Investigator and any designees are responsible for detecting, documenting, and recording events that meet the definition of an AE or SAE. For information on how to follow up AEs, see Section 8.3.3.

8.3.1 Method of detecting adverse events and serious adverse events

Care will be taken not to introduce bias when detecting AEs and/or SAEs. Open-ended and non-leading verbal questioning of the patient is the preferred method to inquire about AE occurrences.

8.3.2 Time period and frequency for collecting adverse event and serious adverse event information

AEs and SAEs will be collected from time of signature of informed consent throughout the treatment period and including the follow-up period (90 days after the last dose of IP). If an event that starts post the defined safety follow-up period noted above is considered to be due to a late-onset toxicity to study drug then it should be reported as an AE or SAE, as applicable.

All SAEs will be recorded and reported to the Sponsor or designee within 24 hours, as indicated in [Appendix B](#). The Investigator will submit any updated SAE data to the Sponsor within 24 hours of the data being available.

Investigators are not obligated to actively seek AE or SAE in former study patients. However, if the Investigator learns of any SAE, including a death, at any time after a patient's last visit and he/she considers the event to be reasonably related to the study drug or study participation, the Investigator may notify the Sponsor.

The method of recording, evaluating, and assessing causality of AE and SAE and the procedures for completing and transmitting SAE reports are described in [Appendix B](#).

8.3.3 Follow-up of adverse events and serious adverse events

During the course of the study, all AEs and SAEs should be proactively followed up for each patient. Every effort should be made to obtain a resolution for all events, even if the events continue after discontinuation or study completion.

Any AEs that are unresolved at the patient's last visit in the study are followed up by the Investigator for as long as medically indicated (this may be beyond the 90 days after the last dose of IP), but without further recording in the eCRF. Any SAE or non-serious AE ongoing at the time of the DCO is to be followed up at the discretion of the Investigator and per local practice and in alignment with the Dosing Modification and Toxicity Management Guidelines (Section [8.4.5](#)), unless the event is considered by the Investigator to be unlikely to resolve or the patient is lost to follow-up. AstraZeneca retains the right to request additional information for any patient with ongoing AE(s)/SAE(s) at the end of the study, if judged necessary.

8.3.4 Adverse event data collection

The following variables will be collected for each AE:

- AE (verbatim)
- The date when the AE started and stopped
- The maximum CTCAE Grade reported

- Changes in CTCAE Grade (report only the maximum CTCAE Grade for the calendar day)
- Whether the AE is serious or not
- Investigator causality rating against the IPs (yes or no)
- Action taken with regard to IPs
- Administration of treatment for the AE
- Outcome

In addition, the following variables will be collected for SAEs:

- Date the AE met criteria for SAE
- Date the Investigator became aware of the SAE
- Seriousness criteria fulfilled
- Date of hospitalisation
- Date of discharge
- Probable cause of death
- Date of death
- Whether an autopsy was performed
- Causality assessment in relation to study procedure(s)
- Causality assessment in relation to other medication, as explained in Section 8.3.5
- Description of the SAE

The grading scales found in the revised NCI CTCAE version 4.03 will be utilised for all events with an assigned CTCAE grading. For those events without assigned CTCAE grades, the recommendation in the CTCAE criteria that converts mild, moderate, and severe events into CTCAE grades should be used. A copy of the CTCAE version 4.03 can be downloaded from the Cancer Therapy Evaluation Program website (<http://ctep.cancer.gov>).

It is important to distinguish between serious and severe AEs. Severity is a measure of intensity, whereas seriousness is defined by the criteria in [Appendix B, B 2](#). An AE of severe intensity need not necessarily be considered serious. For example, nausea that persists for several hours may be considered severe nausea, but not an SAE unless it meets the criteria shown in [Appendix B, B 2](#). On the other hand, a stroke that results in only a limited degree of disability may be considered a mild stroke, but it would be an SAE if it satisfies the criteria shown in [Appendix B, B 2](#).

8.3.5 Causality collection

The Investigator will assess causal relationship between IP and each AE, and answer “yes” or “no” to the question “Do you consider that there is a reasonable possibility that the event may have been caused by the investigational product?”

For SAEs, causal relationship will also be assessed for other medication and study procedures. Note that for SAEs that could be associated with any study procedure, the causal relationship is implied as “yes”.

A guide to the interpretation of the causality question is found in [Appendix B, B 7](#).

8.3.6 Adverse events based on signs and symptoms

All AEs spontaneously reported by the patient or reported in response to the open question from the study site staff, “Have you had any health problems since the previous visit/you were last asked?”, or revealed by observation will be collected and recorded in the eCRF. When collecting AEs, the recording of diagnoses is preferred (when possible) to recording a list of signs and symptoms. However, if a diagnosis is known and there are other signs or symptoms that are not generally part of the diagnosis, the diagnosis and each sign or symptom will be recorded separately.

8.3.7 Adverse events based on examinations and tests

The results from the protocol-mandated laboratory tests and vital signs will be summarized in the CSR. Deterioration as compared to baseline in protocol-mandated laboratory values and vital signs should therefore only be reported as AEs if they fulfil any of the SAE criteria or are the reason for discontinuation of treatment with an IP.

If deterioration in a laboratory value/vital sign is associated with clinical signs and symptoms, the sign or symptom will be reported as an AE, and the associated laboratory result/vital sign will be considered as additional information. Wherever possible, the reporting Investigator uses the clinical, rather than the laboratory term (eg, anaemia versus low haemoglobin value). In the absence of clinical signs or symptoms, clinically relevant deteriorations in non-mandated parameters should be reported as AEs.

Deterioration of a laboratory value that is unequivocally due to disease progression should not be reported as an AE/SAE.

Any new or aggravated clinically relevant abnormal medical finding at a physical examination as compared with the baseline assessment will be reported as an AE unless unequivocally related to the disease under study, see Sections [8.3.9](#) and [8.3.10](#).

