2.3.2.1 Durvalumab (MEDI4736) risks

Risks with durvalumab (MEDI4736) include, but are not limited to, diarrhoea/colitis, pneumonitis/ILD, endocrinopathies (i.e., events of hypophysitis/hypopituitarism, adrenal insufficiency, hyper- and hypo-thyroidism, type I diabetes mellitus [DM] and diabetes insipidus), hepatitis/increases in transaminases, nephritis/increases in creatinine, rash/dermatitis (including pemphigoid), myocarditis, myositis/polymyositis, immune thrombocytopenia, infusion related reactions, hypersensitivity reactions, pancreatitis, serious infections, and other rare or less frequent inflammatory events including neuromuscular toxicities (eg, Guillain-Barre syndrome, myasthenia gravis).

For information on all identified and potential risks with durvalumab (MEDI4736), please always refer to the current version of the durvalumab (MEDI4736) IB.

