6.5 Dose modification

Dose delays are permitted for the management of certain IP-related toxicities as described in the Dosing Modification and Toxicity Management Guidelines (see Section 8.4.5.1 and Dosing Modification and Toxicity Management Guidelines in the Annex document to this CSP). Dose reductions are not permitted.

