9.4 Outcome measures for analyses

- 1 **AE:** Number and proportion of patients with AEs in total and by causality and severity
- 2 **AE:** Number and proportion of patients with Grade 3 and Grade 4 AEs
- 3 **SAE:** Number and proportion of patients with SAEs in total and by causality and severity
- 4 **AEs leading to death:** Number and proportion of patients with AEs leading to death
- 5 **AEs leading to treatment interruption or discontinuation:** Number and proportion of patients with AEs leading to treatment interruption and/or discontinuation
- 6 **AESI:** Defined as an AE of scientific and medical interest specific to understanding of the IP. AESIs for durvalumab (MEDI4736) include, but are not limited to, events with a potential inflammatory or immune-mediated mechanism and which may require more frequent monitoring and/or interventions such as steroids, immunosuppressants and/or hormone replacement therapy. In order to further characterize safety objectives related to AESIs, outcome measures will be assessed, which may include (and are not necessarily limited to) the following:

- (a) Number and proportion of patients with AESIs, by pre-defined type (or newly defined by this study) in total and by seriousness, severity and causality, including immune-relatedness;
 - (b) Number and proportion of patients who received steroids, immunosuppressants and/or hormone replacement therapy to manage AESIs;
 - (c) Time from start of durvalumab (MEDI4736) to the onset of an AESI pre-defined type, all interventions of AESIs by type of intervention (including intervention with steroids, immunosuppressants and/or hormone replacement therapy), and time from onset of an AESI type to resolution;
 - (d) Duration of the intervention with steroids, immunosuppressants and/or hormone replacement therapy until the resolution of AESI;
 - (e) The imAEs will be assessed as a subset of AESIs. An imAE is defined as an AESI that is associated with drug exposure and is consistent with an immune-mediated MOA and where there is no clear alternate etiology.
 - (f) Laboratory findings, vital signs and other safety parameters associated with AESIs will be summarized as part of the AESI outcome measures.
- 7 **PFS:** Defined as the time from the first date of treatment until the date of objective disease progression or death (by any cause in the absence of progression) regardless of whether the patient withdraws from IP or receives another anticancer therapy prior to progression.

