#### 4.5.4 Laboratory Data

Laboratory data obtained up until the 90 days after last dose of study treatment or until the initiation of the first subsequent anti-cancer therapy following discontinuation of study treatment (whichever occurs first) will be used for reporting.

Absolute values and change from baseline for all continuous haematology and clinical chemistry laboratory parameters will be summarised by visit. If a patient does not have the baseline value of laboratory data or the value at visit, the change from baseline is considered as missing.

Shift tables for laboratory values by worst CTCAE Grade will be produced, and for specific parameters separate shift tables indicating hyper- and hypo- directionality of change will be produced. The laboratory parameters for which CTCAE Grade shift outputs will be produced are:

- Haematology: Haemoglobin, Leukocytes, Lymphocytes (absolute count), Neutrophils (absolute count), Platelets
- Clinical chemistry: Alanine transaminase (ALT), Aspartate transaminase (AST), Alkaline phosphatase (ALP), Total bilirubin, Sodium (hypo- and hyper-), Potassium (hypo- and hyper-), Glucose (hypo- and hyper-), and Creatinine

For categorical urinalysis parameters (Bilirubin, Blood, Glucose, Protein), a shift table will be produced comparing baseline value to maximum on-treatment value.

For the parameters with no CTCAE grading that are listed in the CSP the number and percentage of patients with laboratory values outside normal range will be summarized by shift tables from baseline to the post-baseline maximum and minimum value on-treatment.

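### The rule for reporting laboratory abnormalities as AEs can leave related Grade 3/4 laboratory toxicity managed by a dose delay out of the primary endpoint

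*Protocol*

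**What the plan says.** Protocol 8.3.7 deals with deterioration from baseline in the laboratory values that the protocol mandates. Because those results will be summarised in the CSR, they should "only be reported as AEs if they fulfil any of the SAE criteria or are the reason for discontinuation of treatment with an IP". Two further rules follow:

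- Symptomatic cases: "If deterioration in a laboratory value/vital sign is associated with clinical signs and symptoms, the sign or symptom will be reported as an AE". The laboratory result then becomes supporting information.
- Tests outside the schedule: "In the absence of clinical signs or symptoms, clinically relevant deteriorations in non-mandated parameters should be reported as AEs".

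The mandated tests (Protocol Tables 10 and 11) include ALT, AST, bilirubin, creatinine, lipase, amylase, TSH and platelets. Protocol 2.3.2.1 lists among the drug's risks "hepatitis/increases in transaminases, nephritis/increases in creatinine", as well as thyroid disorders, pancreatitis and immune thrombocytopenia. Protocol 6.5 states: "Dose delays are permitted for the management of certain IP-related toxicities".

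SAP 3.2.1 and 4.3 define the primary endpoint as the incidence of Grade 3 and 4 treatment-related AEs up to Day 183. SAP 3.2.3.1 defines such an event as an AE whose relatedness is possible, probable or missing. SAP 3.2.3.3 takes immune-mediated events from the AE page of the CRF. Protocol 9.4 also plans this outcome: "Number and proportion of patients with AEs leading to treatment interruption and/or discontinuation".

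**The concern.** Several of the drug's expected toxicities can first show as an abnormal result in a scheduled blood test, and delaying a dose is a permitted response. If the patient has no symptoms, the event is not serious and treatment later resumes, nothing in 8.3.7 makes it an AE, whatever its grade and however clearly the investigator attributes it to durvalumab. Without an AE record it cannot be a treatment-related AE, an immune-mediated AE or an AE leading to interruption.

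The Grade 3/4 treatment-related rate is the main result of this study. Any loss from the numerator acts in one direction. Sites that follow 8.3.7 to the letter and sites that record such events anyway would also produce rates that are not comparable.

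**Working it through.** **1. Can a laboratory value reach the numerator without an AE record?** No. The endpoint is built from AEs (SAP 3.2.1, 3.2.3.1, 4.3), and no section of either document adds graded laboratory values to it. The SAP 4.5.4 shift tables show worst grade but not causality.

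**2. What happens to a related Grade 3 result in a mandated test?**

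| Course | Route in the documents | Counted? |
|---|---|---|
| No symptoms, not serious, dose delayed, then resumed | No trigger in 8.3.7; only the investigator's choice to record a diagnosis or judge it an important medical event | Not required |
| As above, but treated with steroids | No trigger in 8.3.7; Protocol Table 6 and 8.3.12 treat such cases as AEs; Appendix B2 and B5 may make it serious | Sections conflict |
| Symptoms present | The symptom is the AE, with its own grade (8.3.4, 8.3.7) | Only if the symptom is Grade 3/4 |
| Hy's law case, or treatment stopped because of it | SAE, or the discontinuation trigger | Yes |

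The first row is the clear gap.

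**3. Do other sections agree with 8.3.7?** Not fully. Appendix B1 gives an abnormal laboratory finding as an example of an AE. Protocol 1.2 describes toxicity delays as responses to immune-mediated or other AEs. Protocol 8.3.12 and 8.4.5.1 apply the toxicity guidelines to AEs judged causally related. Each of these presupposes an AE record that 8.3.7 does not require.

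**4. The SAP's own precision figures.** The exact (Clopper-Pearson) limits for x events in n patients are Beta(0.025; x, n−x+1) and Beta(0.975; x+1, n−x). The three intervals in SAP 1.3 reproduce:

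- 10/120 = 8.3% (4.1, 14.8)
- 12/100 = 12.0% (6.4, 20.0)
- 4/30 = 13.3% (3.8, 30.7)

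**5. Effect of missed patients.** Each one lowers the estimate by 100/n points: 100/120 = 0.8, 100/100 = 1.0, 100/30 = 3.3. The table takes the SAP's planning count as what is recorded and adds k missed patients. The values of k are assumptions.

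| Group | k=0 | k=1 | k=2 |
|---|---|---|---|
| n=120 | 8.3% (4.1, 14.8) | 9.2% (4.7, 15.8) | 10.0% (5.3, 16.8) |
| PS 0 to 1, n=100 | 12.0% (6.4, 20.0) | 13.0% (7.1, 21.2) | 14.0% (7.9, 22.4) |
| PS 2, n=30 | 13.3% (3.8, 30.7) | 16.7% (5.6, 34.7) | 20.0% (7.7, 38.6) |

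These intervals reflect sampling error only, not the missed patients.

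**6. A plausibility check.** Protocol 2.3.2.1 gives 3.4% for any Grade 3 or 4 immune-mediated event with durvalumab in PACIFIC, across all organs. In 120 patients that is 0.034 × 120 = 4.1 patients. It is not a strict ceiling: related laboratory toxicity need not be immune-mediated, and the documents do not say which AE rule PACIFIC used. It does argue against assuming a large loss.

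**7. Lipase and amylase.** Both are mandated in Protocol Table 10, but neither is named in the SAP 4.5.4 list for CTCAE shift tables. The fallback shift table is "For the parameters with no CTCAE grading that are listed in the CSP", and the SAP does not say which of the two groups these tests belong to.

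**The case against.** The strongest reply is that 8.3.7 is not a complete bar. Appendix B2 and B5 let an investigator treat an event needing medical treatment as an important medical event, and hence serious. Protocol 8.3.6 prefers a diagnosis to a list of findings, and 8.3.7 prefers the clinical to the laboratory term. Hepatitis, nephritis, hypothyroidism and pancreatitis are named AESIs in 8.3.12. Hy's law has its own route. This stands, and it rules out saying that laboratory toxicity has no way in. But these routes are discretionary or narrow, and none is triggered by a Grade 3 result with a dose delay.

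A reader might infer that steroid-treated cases are barred too. The documents do not support that: Protocol Table 6 allows immunosuppressants for AEs related to the product, so such a case is already an AE in the protocol's own terms. What remains is a conflict with 8.3.7 that sites may resolve differently.

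A reader might also infer that Grade 3/4 laboratory toxicity is always managed by delay. The rules for delay and permanent discontinuation are in the toxicity annex, which is not among the documents, and discontinuation does trigger reporting.

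The different treatment of mandated and non-mandated tests can be defended, since mandated results are tabulated anyway. SAP 4.5.4 summarises all continuous chemistry values by visit, including lipase and amylase. Graded shifts, liver-enzyme bands, TSH tables and reasons for dose delay are also planned. That discloses the abnormalities but supplies no causality, so it cannot repair this endpoint.

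**Conclusion.** The point holds in limited form. Followed as written, Protocol 8.3.7 allows a related, non-serious Grade 3 (less often Grade 4) laboratory toxicity without symptoms, managed by dose delay, to be left out of the primary endpoint, the immune-mediated AE tables and the interruption outcome. The effect on the primary rate is downward. That Grade 4 cases are more often judged serious is an expectation; the documents give no data on it. For steroid-treated cases the fault is inconsistency between sections, with possible differences in capture between sites.

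The size is unknown. What can be stated is the loss per missed patient: 0.8 points at n=120, 1.0 at n=100 and 3.3 at n=30. A reader might assume that 1% to 4% of patients are affected and conclude that the rate is understated by up to a third (at n=150, 4% is 6 patients, and 18/150 = 12.0% would read 12/150 = 8.0%). The documents do not support that: they give no such frequency, and 4% exceeds the 3.4% reported in PACIFIC for all Grade 3/4 immune-mediated events.

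The study tests no hypothesis, so no decision rule is affected. What is at stake is the accuracy of the primary estimate.

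**What to change.** 1. **Reconcile Protocol 8.3.7** with Appendix B1, 6.4, 6.5 and 8.3.12. A deterioration in a mandated laboratory value should also be reported as an AE, with causality, when it leads to a dose delay or interruption, is treated, or is clinically relevant in the investigator's judgement.
2. **Query the data before database lock.** List each on-treatment Grade 3/4 laboratory value that coincides with a dose delay or steroid start, and ask the site whether an AE record is missing. Report the primary rate both as first recorded and after the query, because causality assigned late is a different form of ascertainment.
3. **Pre-specify a supportive analysis** of all-cause treatment-emergent Grade 3/4 laboratory values to Day 183, shown beside the primary endpoint, and state the ascertainment limitation in the CSR.
4. **Add lipase and amylase** to the CTCAE shift list in SAP 4.5.4.

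Items 2 and 3 matter most. Protocol 1.1 estimates last patient completion in Q2 2023. Taking off 24 months plus 90 days (about 27 months) puts the last treatment start near Q1 2021 and the end of its six-month window near Q3 2021, before the SAP version of 1 October 2021. On that estimate, an amendment alone would do little for the primary endpoint.

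The cost is a short protocol clarification, CRF guidance, one data-review listing and a few tables. There are no new tests or visits, and patient management does not change. The downsides are a few more AE entries, a slightly higher reported rate and some late causality assessments.
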